6. INTERVENTION

Children were given 200 mL of milk with after the breakfast every day, for five days a week. First, the children will drink milk without probiotic, during the 3-months period. And then the children drink milk with probiotic during the 3-months period (*L. rhamnosus* and *B. longum*). The nursery school staff prepared the commercial milk with researcher supervision. The milk will be prepared with safe water (packaged water).

6. After the intervention with each milk, the next outcome measures:

6.1 Index dental plaque Sillness and Löe.

6.2 Collection of saliva: Each child will accumulate saliva and then collect it in sterile containers (approximately 1.5-2 ml).

6.3 1 ml of saliva with glycerol (10%) will be frozen (-20°C) in microcentrifuge tubes (1.5ml). This sample is for microbiological analysis of *S. mutans*).

6.4 With the other 1ml is to determine the pH. The Salivary pH will be determined with pHmeter Fisherbrand Accumet Portable AP110.6.5 Rinse with 10% sugar solution. The children will make a mouthwash with sugar

solution and they will wait 5 minutes. Finally, the pH of the saliva is will be determined again.

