PROTOCOL

**Effect of *Lactobacillus rhamnosus* GG and
Bifidobacterium longum in children aged 3 to 5 years of
Villavicencio and Pasto.**

ClinicalTrials.gov ID: NCT03078179

Principal Investigator: [name]

Sponsor: Universidad Cooperativa de Colombia

Funded by: 1. Universidad Cooperativa de Colombia

2. Colgate

Version number: 5

17 June 2015

Adapt: 01 August 2016

Table of contents

1. Synopsis.....	2
2. Introduction	3
3. Schema	4
4. Schedule of activities.....	5
5. Study Description	6
6. Risk/Benefit assessment	7
7. Objectives and Endpoints.....	8
8. Study Design.....	10
8 Study Population	14
9 Study intervention.....	15
10 Statistical considerations	18
11. Regulatory, ethical, and study oversight consideration.....	20
12. References.....	21

1.Synopsis

Study Type	Interventional, Pilot Study
Intervention	
 1. Commercial Cow Milk with Probiotic (Lactobacillus rhamnosus and Bifidobacterium longum) 2. Commercial cow milk without probiotic
Study Design:	Repeated measures design.
Allocation:	Nonrandomized
Endpoint Classification	Efficacy Study
Intervention Model:	Crossover study
Masking:	No masking
Sample size	Convenience sampling
Primary Purpose	Treatment trial
Subjects:	Three to five-year-old children
Genders:	Both
Sites	Kindergarten in Villavicencio y Pasto, Colombia
Study duration	12 months
Objective	To determine the effect of consumption of commercial milk beverages enriched with Lactobacillus rhamnosus y Bifidobacterium longum on the incidence of caries in children aged 3 to 5 years.

[figure not shown]
2.Introduction

Several bacterial strains have been studied as probiotics, either isolated or in combination, as well as the doses used in studies, intervention periods, populations, experimental designs, and routes of administration. The results often include a decrease in *S. mutans* count in saliva or plaque, but few studies conduct dental clinical examinations to assess treatment. This is confirmed by a meta-analysis conducted by Laleman et al in 2013, claiming that the scientific evidence demonstrating caries control is insufficient (1). However, the results of studies describing the effect of probiotics in the index of carious lesions (2,3) or dental plaque, are promising (4,5).

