The probiotics most commonly evaluated so far in the oral cavity are isolated microbial strains, mainly of the digestive tract, like the ones belonging to the genus *Lactobacillus* (*L. rhamnosus*, *L. reuteri*, *L. casei*, *L. brevis*, *L. paracasei*, *L. acidophilus*, *L. plantarum*) and *Bifidobacterium* (*B. bifidum*, *B. longum*, *B. lactis*, *B. animalis*, *B. infantis*) (6,7). These bacteria have proven their safety for many years, allowing clinical studies and the development of commercial products, with the added value that some have been identified in healthy individuals (DMF = 0) (*L. rhamnosus*, *L. plantarum*, *L. acidophilus*, *L. brevis*, *L. paracasei*) (8), suggesting their role in micro-ecologic balance.

One of the most commonly studied probiotic bacteria in the oral cavity was isolated by Gorbach and Godin in 1983 from digestive tract of a healthy adult (9). It was named *Lactobacillus rhamnosus* GG (ATCC53103) and is characterized by inhibiting, by means of bacteriocins, a wide variety of human pathogenic bacteria (10), including *S. mutans*, *S. sobrinus*, *Aggregatibacter actinomycetemcomitans*, *Porphyromonas gingivalis* and *Prevotella intermedia*. In addition, this bacterium colonizes the microcosm of saliva, and has no cariogenic effect. This bacterium was used to conduct one of the most complete clinical studies in children (aged 1 to 6 years), reducing the incidence of caries in the age of 3 to 4 years (2).

3.Schema

4. Schedule of activities

Activities	Months											
	1	2	3	4	5	6	7	8	9	10	11	12
Parents meeting	■											
Informed consent		■										
Personal interview		■										
Clinical diagnosis			■									
Selection criteria			■									
Begin: diagnostic tests				■								
Intake milk without probiotic for 3 months				■	■	■						
Ending: diagnostic tests							■					
Intake milk with probiotic for 3 months							■	■	■			
Ending: diagnostic tests										■		
Analysis of information											■	■

5. Study Description

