Brief Summary: The objective of this study is to determine if the presence of bacteria with probiotic characteristics (*Lactobacillus rhamnosus* GG and *Bifidobacterium longum*) in a commercial milk, control some measures that indicate cariogenic processes. **Detailed Description:** Dental caries is a disease caused by a shift in pH balance, resulting in the formation of a biofilm composed mainly of cariogenic microflora. The interaction between this microflora and host factors conditions the deceleration or acceleration of the disease. Some biotechnology tools have been tried based on all this research, including probiotics, intended for a selective control of the etiological agents of caries and the maintenance of oral homeostasis. **Methodology:** In this study, preschool children belonging to public kindergarten in Villavicencio and Pasto, Colombia will be invited to participate. After obtaining parent's informed consent, the children will start commercial milk intake without probiotic for 3 months (*Klim fortificada Nestlé*). One week after, they will start commercial milk with probiotic during others 3 months (*nanPro3 Nestlé*). Clinical and microbiological testing of saliva at baseline, 3 m, and 6m will be performed. Differences in salivary pH (before and after a sugar solution), remineralization and demineralization in early Stage Decay and Established decay tooth (according to ICDAS) and quantification of Streptococci of the mutans group. **Expected results:** Statistically significant decrease in pH drop, demineralization in decay tooth and quantification of Streptococci of the mutans group.

6.Risk/Benefit assessment

Minimal Risk:

This study has a minimal risk because the probability and magnitude of possible harms implied by participation in the research is no greater than those encountered by participants in the aspects of their everyday life that relate to the research (TCPS Chapter 2B). The intervention is safe because the study will use two commercial milk with Sanitary Registry of health products. During the reconstituting of powdered milk, the person responsible will use bottled water and good hygienic conditions. Moreover, during the clinical diagnostic and the clinical laboratory, this research will practice principles and practice about biosafety.

Benefit:

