The immediate potential benefits of this research with children, is the daily intake of two nutritive commercial milk, for 6 months. Also, the researcher gives information about the oral health, the presence of caries, and the requirements of specific treatment.

7.Objectives and Endpoints

OBJECTIVES	ENDPOINTS	Justification for endpoints
To determine the effect of consumption of milk beverages enriched with Lactobacillus rhamnosus and Bifidobacterium longum in diagnodent measurement.	Diagnodent measurement of tooth decay lesions (ICDAS 1-4). The idea is to compare the effect of probiotics in children during the intake of milk without probiotic versus during the intake of milk with probiotic.	DIAGNOdent is a laser fluorescence device used for dental caries diagnosis in occlusal and smooth surfaces. Diagnodent measurement allows knowing if the effect of probiotic suppresses the demineralization of the cariogenic lesion. The reason is, if the probiotic inhibit the cariogenic bacteria, reduce the demineralization and improve the mineralization
To determine the effect of consumption of milk beverages enriched with Lactobacillus rhamnosus and Bifidobacterium longum in the change of pH of saliva after a rinse with sugar.	For this objective, the purpose is to compare the points difference between salivary pH before and after a rinse with sugar, in children during the intake of milk without probiotic versus during the intake of milk with probiotic	The scientific literature shows when there are many cariogenic bacteria, the drop of Ph after a rinse with sugar is greater compared with people who have less cariogenic bacteria levels.
To determine the effect of consumption of milk beverages enriched with Lactobacillus rhamnosus y Bifidobacterium longum in the concentration of group mutans streptococci in saliva.	The comparison of the quantification of group mutans streptococci from saliva, during the intake of milk without probiotic versus during the	Other studies have shown the inhibition of Lactobacillus rhamnosus in Streptococcus mutans .

	intake of milk with probiotic	

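### Every child takes control milk first and probiotic milk second with no concurrent group, so the likely paired contrast cannot separate milk from time, yet 7.1 and the section 7 justification credit the probiotic and the Synopsis calls the study a crossover

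*Combined protocol and SAP*

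**What the plan says.** - **Order.** Section 7.7, step 6 fixes one sequence for everyone: "First, the children will drink milk without probiotic, during the 3-months period. And then the children drink milk with probiotic during the 3-months period". The schedule in section 4 and the summary in section 5 give the same order.
- **Design labels.** The Synopsis gives the intervention model as "Crossover study". Section 7.2 describes one group followed before and after, without randomisation. No section describes a second sequence or a parallel group.
- **Readings.** Sections 5 and 9 give three: baseline, the end of control milk (3 months) and the end of probiotic milk (6 months).
- **Analysis.** Section 11 (Statistical analysis) names the paired t-test, Wilcoxon or McNemar. It does not say which two readings are paired, and it has no term for period or for any covariate.
- **Attribution.** The four hypotheses in 7.1 say that the probiotic milk reduces each outcome. Section 7 justifies the primary endpoint thus: "Diagnodent measurement allows knowing if the effect of probiotic suppresses the demineralization of the cariogenic lesion". Section 5 expects a "Statistically significant decrease in pH drop, demineralization in decay tooth and quantification of Streptococci of the mutans group".
- **Influences that can change over time.** In 8.4 parents are to report antibiotics, fluoride from another dentist, antiseptic or mouthwash, and better brushing. Under Benefit in section 6, "the researcher gives information about the oral health, the presence of caries, and the requirements of specific treatment"; the timing is not stated.

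**The concern.** Pairing removes differences between children. It does not remove anything that changes in the same children between month 3 and month 6. Because every child moves from control to probiotic milk over the same interval, any such change is counted as a milk difference. The protocol itself lists several candidates, and the analysis uses none of them.

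At stake is what the trial may conclude on its primary outcome and all three secondary outcomes. With the present wording, a significant 3-to-6-month fall would be reported as a reduction caused by the probiotic. The crossover label adds to this, because readers expect a crossover to balance period effects, and a single sequence cannot.

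**Working it through.** **Which pair is tested?** Section 7 compares intake without probiotic against intake with probiotic. Table 1 lists values before and after, for control and intervention. With three readings, the 3-month value is both the end of control milk and the start of probiotic milk. End of control against end of probiotic, and before against after probiotic, are therefore the same contrast: 6 months minus 3 months. This is an inference, since section 11 does not name the pair.

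**What that contrast estimates.** Let b be the baseline level, d the drift per period, c the shift from control milk and p the shift from probiotic milk, with no carry-over. The three readings are b, b + c + d and b + p + 2d. Then

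6 m − 3 m = (b + p + 2d) − (b + c + d) = (p − c) + d.

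The milk difference p − c and the drift d enter only as a sum.

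**Illustrative size.** The plan gives no sample size, SD, effect size or drift, so there is no figure of its own to reproduce. Alpha is 0.05 (section 11); I assume a two-sided test. Let δ be the drift in SDs of the paired difference, with p = c. The rejection rate is P(|T| > t) with t the 0.975 quantile on n − 1 degrees of freedom and T noncentral t with noncentrality δ√n. For n = 40, t = 2.023 and δ√n = 0.632, 1.265, 1.897 and 3.162 for δ = 0.1, 0.2, 0.3 and 0.5.

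| n (assumed) | δ = 0.1 | δ = 0.2 | δ = 0.3 | δ = 0.5 |
|---|---|---|---|---|
| 20 | 0.071 | 0.136 | 0.247 | 0.565 |
| 40 | 0.095 | 0.235 | 0.457 | 0.869 |
| 60 | 0.119 | 0.332 | 0.628 | 0.968 |
| 100 | 0.168 | 0.508 | 0.844 | 0.999 |

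A larger sample makes this worse. In the other direction, take a true effect of 0.5 SD at n = 40, with power 0.869. Opposite drift of 0.1, 0.2 or 0.3 leaves a net 0.4, 0.3 or 0.2, and power falls to 0.694, 0.457 or 0.235.

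**Does the baseline reading rescue it?** The obvious candidate is the change in the probiotic period minus the change in the control period:

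(6 m − 3 m) − (3 m − baseline) = (p − c + d) − (c + d) = p − 2c.

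Equal drift cancels, but the result is not p − c. If a fraction k of the control effect persists to 6 months, the contrast is p − (2 − k)c. It equals p − c only if c = 0 or k = 1. If the milks act equally (p = c) and nothing carries over, it equals −c.

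Under compound symmetry with variance σ² and correlation ρ, its variance is (1 + 4 + 1)σ²(1 − ρ) = 6σ²(1 − ρ), against 2σ²(1 − ρ) for 6 m − 3 m: three times as large. At n = 40 with p = c, the noncentrality is c√(40/3) = 0.730, 1.095 and 1.826 for c = 0.2, 0.3 and 0.5 SD of the paired difference. It rejects in 11, 19 and 43% of trials although the milks do not differ. For a true 0.5 SD effect with c = 0, its power is 43% instead of 87%, and 80% power needs 97 children instead of 34.

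**The case against.** **The design is disclosed.** The Synopsis says pilot, nonrandomised, repeated measures and unmasked, and 7.2 says one group. This stands: nothing is concealed, and the fault is not the choice of a single-group pilot. Disclosing the allocation does not, however, support the causal wording in 7.1 and section 7.

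**Not all the wording is causal.** A reader might infer that every objective and hypothesis must be rewritten. The documents do not support that. An objective that begins "To determine the effect of consumption of commercial milk beverages enriched with" poses a question. H01 to H04 are null statements of no difference between milks, which 6 m − 3 m does address once it is named. The expected results in section 5 are an expectation.

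**Control first has a reason.** The Introduction says of the *L. rhamnosus* strain that "this bacterium colonizes the microcosm of saliva", so giving the probiotic second avoids its carry-over into the control period. That is a fair reason for the order, and this point does not ask for it to be changed. It does nothing about drift.

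**The size is hypothetical.** This is correct. The sample size and every drift above are assumptions, and drift could run either way.

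**Conclusion.** The point holds as a matter of attribution and specification. From the order and the single group alone, 6 months minus 3 months equals the milk difference plus whatever changed with time, and no analysis of those two readings separates them. This needs no numerical assumption beyond reading the pair from section 7.

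The size does rest on assumptions. At an assumed 40 children with no milk effect, drift of 0.1 to 0.5 SD of the paired difference raises the false-positive rate from 5% to between 10% and 87%. Opposite drift of 0.1 to 0.3 cuts power for a 0.5 SD effect from 87% to between 69% and 24%. These figures are for the t-test. The same confounding applies to the plaque comparison by McNemar's test, for which no size is computed.

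Two stronger readings are tempting and should not be drawn. One is that the result will be biased by a known amount or in a known direction: the documents give neither. The other is that comparing the change in each period solves the problem: it does so only with equal drift and a control milk that either has no effect on the reading or has an effect that fully persists.

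**What to change.** 1. In the Synopsis and 7.2, describe the design as: *single-group, fixed-sequence before-and-after study; control milk, then probiotic milk; no concurrent control*. Remove the crossover label.
2. In section 11 (Statistical analysis), name 6 months minus 3 months as the tested contrast for H01 to H04.
3. Reword 7.1 and the section 7 justification as a change between the end of the control-milk period and the end of the probiotic-milk period. Add to section 11: *Because all children receive the milks in the same order without a concurrent group, a difference will not be attributed to the probiotic alone.*
4. Tabulate the 8.4 events by period beside the result.
5. Do not add the change-versus-change contrast as a remedy. If it is wanted as a descriptive DIAGNOdent sensitivity analysis, state its conditions (equal drift; control milk without effect, or with an effect that fully persists), that with no carry-over it estimates p − 2c, and that its variance is about three times as large under compound symmetry. State also that regression to the mean affects it if baseline is the screening reading that had to exceed 7 (7.7, step 3.2).
6. Reconcile the baseline timing. Section 4 puts "Begin: diagnostic tests" in month 4, after diagnosis and selection in month 3, while 7.7 places plaque and saliva sampling on the second day, with prophylaxis on the first. If baseline samples do follow prophylaxis by a day, the change-versus-change contrast should not be used for plaque or saliva, because at 3 and 6 months those samples come before prophylaxis.

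The cost is a weaker stated conclusion. No extra children, visits or measurements are needed.

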6.6 Dental prophylaxis

6.7 ICDAS

6.8 Clinical assessment of demineralization with Diagnodent.

8 Study Population

8.1 General information: children from 3 to 5 years of kindergartens

8.2 Inclusion criteria:

- Pre-school children from age 3 to 5.
- Healthy children from a general health perspective, with early stage decay and established decay

8.3 Exclusion criteria

- Children with systemic disorders who need special care and/or who have the intolerance to milk drinks or allergy to any of the components of the experimental and/or the placebo beverage.
- Children who don't like milk.
- Children with severe decay

8.4 Lifestyle consideration:

The children's parent will inform when:

- The child uses antibiotic
- The child visits another dentist and the dentist use Fluor.
- The child uses an antiseptic or mouthwash.
- The child improves the brush frequency.

9 Study intervention

Primary Outcome Measure:

1. Change in remineralization of tooth decay

DIAGNOdent peak reading in three moments, at the beginning and at the end of the milk without probiotic (after 3 months), and at the end of the milk with probiotic (after 3 months) (Table 1).

Secondary Outcome Measures:

1. Change of salivary pH after a rinse with sugar.

Change pH after a rinse with sugar (point of difference), in three moments, at the beginning and at the end of the milk without probiotic (after 3 months), and at the end of the milk with probiotic (after 3 months) (Table 1).

2. Change of Dental Plaque Index

Silness-Löe plaque index in three moments, at the beginning and at the end of the milk without probiotic (after 3 months), and at the end of the milk with probiotic (after 3 months) (Table 1).

3. Change of concentration of group mutans streptococci in saliva

Colony Forming Units (CFUs) determination in three moments, at the beginning and at the end of the milk without probiotic (after 3 months), and at the end of the milk with probiotic (Table 1).

TABLE 1.

Variable	Scale of measurement	Data	Type of variable	Measure Type	Measure of dispersion
BEFORE (Control and Intervention)					
Diagnodent measurement	Quantitative	Values 0-99	Dependent	-Mean -Median	-Standard deviation -Inter-Quartile range
Change of salivary pH after a rinse with sugar.	Quantitative	Point of difference	Dependent	-Mean -Median	-Standard deviation -Inter-Quartile range
Dental Plaque Index	Qualitative	0=absent 1=present	Dependent	Frequency	NA
Colony Forming Units of the group mutans streptococci	Quantitative	UFC	Dependent	-Mean -Median	-Standard deviation -Inter-Quartile range
AFTER (Control and Intervention)					
Diagnodent measurement	Quantitative	Values 0-99	Dependent	-Mean -Median	-Standard deviation -Inter-Quartile range

Change of salivary pH after a rinse with sugar.	Quantitative	Point of difference	Dependent	-Mean -Median	-Standard deviation -Inter-Quartile range
Dental Plaque Index	Qualitative	0=absent 1=present	Dependent	Frequency	NA
Colony Forming Units of the group mutans streptococci	Quantitative	UFC	Dependent	-Mean -Median	-Standard deviation -Inter-Quartile range

10 Statistical considerations

Statistical hypothesis

Primary Efficacy

H01: There is no significant difference of consumption of commercial milk beverages enriched with *Lactobacillus rhamnosus* and *Bifidobacterium longum* in diagnodent measurement in comparison with commercial milk without probiotic.

Secondary Efficacy

H02: There is no significant difference of consumption of commercial milk beverages enriched with *Lactobacillus rhamnosus* and *Bifidobacterium longum* in change of pH of saliva before and after a rinse with sugar, in comparison with commercial milk without probiotic.

H03: There is no significant difference of consumption of commercial milk beverages enriched with *Lactobacillus rhamnosus* and *Bifidobacterium longum* in concentration of group mutans streptococci in saliva in comparison with commercial milk without probiotic.

H04: There is no significant difference of consumption of commercial milk beverages enriched with *Lactobacillus rhamnosus* and *Bifidobacterium longum* in dental plaque index in comparison with commercial milk without probiotic.

11 Statistical analysis

Data will be organized with Microsoft Excel. The analyses will be performed using the program SPSS® Statistics 25.0 version. Univariate descriptive

analyses: means, standard deviations, medians, and interquartile ranges according to the normality. Data comparisons will be performed with Students t-test for related samples. A p-value <0.05 was considered as statistically significant. If there are not data normally distributed, the comparison will be with Wilcoxon test. In the case qualitative variable (Dental plaque index), the comparison will be with McNemar's test.

11. Regulatory, ethical, and study oversight consideration

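### Only paired tests are named for a three-reading design with no missing-data rule; if loss after month 3 depends on the month-3 reading, the completers' milk contrast is biased

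*Combined protocol and SAP*

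**What the plan says.** The synopsis labels the trial "Repeated measures design". Section 5 states: "Clinical and microbiological testing of saliva at baseline, 3 m, and 6m will be performed". Section 9 defines the primary outcome as "DIAGNOdent peak reading in three moments": the start, the end of the milk without probiotic and the end of the milk with probiotic. The three secondary outcomes follow the same scheme. The order of the milks is fixed, without probiotic first (section 8, item 7.7, intervention step).

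Section 11 (Statistical analysis) names three tests:

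- quantitative outcomes: "Data comparisons will be performed with Students t-test for related samples";
- non-normal data: "If there are not data normally distributed, the comparison will be with Wilcoxon test";
- plaque: "In the case qualitative variable (Dental plaque index), the comparison will be with McNemar's test".

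The criterion is "A p-value <0.05 was considered as statistically significant", with sidedness not given. The documents do not say which readings form the pair. They also give no sample size, expected loss, missing-data rule, analysis set or sensitivity analysis. Deletion of incomplete pairs is not written down; it follows from the tests named.

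**The concern.** Each named test needs a complete set of the compared readings. If the pair is month 6 against month 3, a child who leaves after month 3 contributes nothing, although the baseline and month-3 readings are on file. Because the probiotic milk always comes second, loss after month 3 always removes the probiotic reading.

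If the children who leave tend to have high month-3 readings, those who stay have an unusually low month-3 mean. Their month-6 mean moves back towards the average, so the paired difference shows a rise that the milk did not cause. On DIAGNOdent a higher value is worse, so this works against the probiotic milk. Loss of the children with the lowest month-3 readings works in its favour by the same mechanism.

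The documents contain possible routes for such loss. Families are told about caries and the need for treatment (section 6). The primary endpoint covers only ICDAS 1-4 lesions (section 7), while ICDAS is scored again after each milk. Parents report antibiotic, fluoride or mouthwash use and changed brushing (item 8.4), with no stated consequence for the analysis. None of these passages says that readings will be lost.

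**Working it through.** The plan has no figure to reproduce: it states no sample size, SD, effect size, power or loss rate. What follows is an illustration.

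**Assumed inputs.** Three readings per child (from section 9), each with SD 1; equal correlation rho between any two readings, 0.4 to 0.8; no true difference between the milks; loss only of the month-6 reading, near 20%. The simulations of test error also assume 60 children.

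**1. Highest month-3 readings lost outright.** If the top share d is lost, the mean month-3 reading of those who stay is −phi(c)/(1−d), where c is the upper-d normal quantile. Their expected month-6 mean is rho times that value. So

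bias of (6 m − 3 m) = (1 − rho) × phi(c)/(1 − d).

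For d = 0.20, c = 0.842 and phi(c) = 0.280, and 0.280/0.80 = 0.35.

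- rho 0.4: 0.6 × 0.35 = 0.21 SD
- rho 0.6: 0.4 × 0.35 = 0.14 SD
- rho 0.8: 0.2 × 0.35 = 0.07 SD

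**2. Graded loss.** Here the chance of loss rises with the month-3 reading on a logistic scale. Simulation with 22% loss gave completer biases of 0.117, 0.073 and 0.037 SD at rho 0.4, 0.6 and 0.8. A steeper dependence (log-odds slope 1.5 per SD) with 20% loss gave 0.136, 0.094 and 0.046 SD. In that second setting, with 60 children, the paired t-test rejected a true null in 13.7%, 11.6% and 8.7% of trials against a nominal 5%. A likelihood-type estimate, which regresses month 6 on baseline and month 3 and averages over all children, stayed within 0.004 SD of zero.

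**3. Other loss mechanisms** (rho 0.6, 20% loss, 60 children):

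| Loss depends on | Paired bias (SD) | Paired type I error | All-readings bias (SD) |
|---|---|---|---|
| nothing (random) | −0.003 | 0.056 | −0.003 |
| baseline only | −0.003 | 0.051 | −0.003 |
| month 3 | +0.094 | 0.116 | +0.004 |
| unseen month 6 | −0.091 | 0.119 | −0.137 |

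Loss on baseline alone cancels because, under equal correlations, baseline predicts month 3 and month 6 equally. When loss depends on the unseen month-6 value, the all-readings estimate does worse than the paired test. It restores the month-3 mean to that of all children, while the month-6 mean is still too low.

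**4. If the pair is change against change.** The quantity is (6 m − 3 m) − (3 m − baseline), in which month 3 enters twice. The bias under step 1 doubles: at rho 0.6, 2 × 0.4 × 0.35 = 0.28 SD.

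**The case against.** The strongest objection is that the pair is not defined. Item 7.2 describes a controlled before-and-after study, section 9 titles the outcomes as changes, and Table 1 has before and after blocks for control and intervention. A paired test of change on one milk against change on the other would use all three readings. Section 7, which compares readings taken under the two milks, fits month 6 against month 3. The ambiguity stands and needs one sentence in the plan. It does not remove the missing-data problem: a change-against-change test needs all three readings, and step 4 shows a larger bias.

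Three stronger conclusions are tempting, and the documents do not support them.

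- *The repeated-measures label makes the paired test wrong.* H01 to H04 each compare two milks, and a within-child paired test is valid for that when the data are complete.
- *The milk contrast will be biased.* No passage reports or predicts loss tied to a reading. Nursery staff prepare the milk at the kindergarten, and children who dislike milk are excluded at entry. Random loss, and baseline-driven loss under equal correlations, give no bias.
- *A mixed model cures dropout.* It corrects only loss explained by readings on file.

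It is also fair to say that losing exactly the top 20% is an extreme rule, and that in a convenience-sample pilot with a fixed order milk is confounded with period whichever model is used.

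**Conclusion.** The point holds as a conditional one. The gap is the absence of any rule, or any analysis, for children with incomplete readings; the paired test itself is not at fault. If loss after month 3 depends on the month-3 reading, the completers' difference is off by roughly 0.04 to 0.12 SD with graded loss near 20% (up to 0.14 SD if the dependence is steeper). It is off by 0.07 to 0.21 SD if the highest fifth is lost outright. The sign depends on which children leave. Loss rate, correlation, mechanism and the 60 children are all assumed, so the size and direction in this trial are unknown. The change is still worth making because it costs little and gives up nothing when no reading is missing.

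**What to change.** In section 11 (Statistical analysis):

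1. State that the primary contrast is end of probiotic milk (6 m) minus end of control milk (3 m). If change against change is intended, state that explicitly and define the contrast to match.
2. Analyse DIAGNOdent, pH drop and log-transformed CFU with a linear mixed model (SPSS MIXED, in the software already named). Use visit as a fixed factor and an unstructured within-child covariance, and include every child with at least one reading. Define one DIAGNOdent summary value per child per visit, since a child may have several lesions, and give a rule for zero CFU counts.
3. Keep the paired t-test or Wilcoxon test on completers as a sensitivity analysis, and as the check when residuals are clearly non-normal.
4. Keep McNemar's test for plaque, and state that it uses complete pairs only.
5. Add a delta-shift sensitivity analysis: shift the imputed month-6 values over a pre-set range in both directions and report where the conclusion changes.
6. Report the number missing and the reasons at each visit, for each outcome.

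The cost is plan wording and some extra SPSS work. With no missing readings, the model's contrast and standard error equal those of the paired t-test. The downside is reliance on missing-at-random: the model does not correct loss driven by the unseen month-6 value, which is why item 5 is needed. Nothing here separates milk from period; that limit of the fixed order remains and should be stated with the results.
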